expansion of the AXR-159 Ophthalmic Solution 50 mg/mL and vehicle TID groups (N = 45 per group) and to halt the initiation of Stage 1, Cohorts 2 and 3. If AXR-159 Ophthalmic Solution 50 mg/mL TID is NOT safe and well tolerated the DRC will recommend Stage 1, Cohort 2 (8 patients on AXR-159 Ophthalmic Solution 30 mg/mL TID and 2 patients on vehicle TID) and to halt the Cohort 1 Expansion Cohort. Patients already enrolled in Stage 1, Cohort 1 will continue at the investigator's discretion. Any patients that discontinue during the study will be followed through the resolution of their adverse event(s) or end of study. When the 10th patient enrolled in Stage 1, Cohort 2 completes the Week 2 visit, a DRC will evaluate all available safety data. If AXR-159 Ophthalmic Solution 30 mg/mL TID is safe and well tolerated the DRC will recommend expansion of the AXR-159 Ophthalmic Solution 30 mg/mL and vehicle TID Expansion Cohort (N = 40 per group) and to halt Cohort 3. If AXR-159 Ophthalmic Solution 30 mg/mL TID is NOT safe and well tolerated the DRC will recommend Stage 1, Cohort 3 (8 patients on AXR-159 Ophthalmic Solution 30 mg/mL BID and 2 patients on vehicle BID) and to halt the Cohort 2 Expansion Cohort. Patients already enrolled in Stage 1, Cohort 2 will continue at the investigator's discretion. When the 10th patient enrolled in Stage 1, Cohort 3 completes the Week 2 visit, a DRC will evaluate all available safety data. If AXR-159 Ophthalmic Solution 30 mg/mL BID is safe and well tolerated the DRC will recommend expansion of the AXR-159 Ophthalmic Solution 30 mg/mL and vehicle BID Expansion Cohort (N = 35 per group). If AXR-159 Ophthalmic Solution 30 mg/mL BID is NOT safe and well tolerated the DRC will recommend stopping the study. Thus, in stage 1 a successive cohort will only be started if the previous cohort is felt to be either unsafe or poorly tolerated by the DRC.

When the last patient enrolled in Stage 1 completes the Month 3 visit in the Expansion Cohort, a formal Interim Analysis will be completed and the DRC will evaluate all available safety and efficacy data from Stage 1 before recommending initiation of Stage 2. Stage 2 is a parallel group design and the DRC may recommend up to a maximum of 7 groups as depicted in [Figure 6.1-1](#). Groups that are either unsafe, poorly tolerated, or likely futile may be discontinued by the DRC. The DRC may reallocate patients to the surviving AXR-159 Ophthalmic Solution dose groups.

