11.5 Type and Duration of the Follow-up of Subjects after Adverse Events

Any serious adverse event occurring during the study period (beginning with informed consent) and for at least 12 weeks after the last dose of study drug must be immediately reported, but no later than 24 hours after learning of a serious adverse event. Serious adverse events must be reported to AxeroVision Inc. (or Agent of AxeroVision Inc.) as listed on the AxeroVision Inc. Study Contacts Sheet and recorded on the serious adverse event form. All patients with a serious adverse event must be followed up and the outcomes reported. The investigator must supply AxeroVision Inc. and the IRB/IEC with any additional requested information (e.g., autopsy reports and discharge summaries).

In the event of a serious adverse event, the investigator must:

1. Notify AxeroVision Inc. immediately by fax or email using the serious adverse event form (contact details can be found on page 1 of the serious adverse event form); phone numbers and relevant AxeroVision Inc. personnel contacts are also on the front page of the protocol.
2. Obtain and maintain in his/her files all pertinent medical records, information, and medical judgments from colleagues who assisted in the treatment and follow-up of the patient.
3. Provide AxeroVision Inc. with a complete, written description of the adverse event(s) on the serious adverse event form describing the event chronologically, including any treatment given (e.g., medications administered, procedures performed) for the adverse event(s). Summarize relevant clinical information about the event: signs, symptoms, diagnosis, clinical course and relevant clinical laboratory tests, etc. Include any additional or alternative explanation(s) for the causality which includes a statement as to whether the event was or was not related to the use of the investigational drug.

4. Promptly inform the governing IRB/IEC of the serious adverse event as required by the IRB/IEC, local regulations, and the governing health authorities.

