12.4.7 Safety Variables

Safety measures will be analyzed using the safety population. Medical Dictionary for Regulatory Activities (MedDRA) nomenclature will be used to code adverse events. Incidence rates of each treatment-emergent adverse event will be summarized by primary system organ class and preferred term. Summary tables will be generated for all treatment-emergent adverse events regardless of causality as well as for those considered to be treatment-related.

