7.4 Safety

The Safety population includes all randomized subjects who have received at least one dose of the investigational product. The Safety population will be analyzed for all safety assessments. Subjects in the Safety population will be analyzed as treated.

8. General Statistical Considerations

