The investigator should initially classify the expectedness of an AE, but the final classification is subject to the Medical Monitor's determination.

An AE is considered serious if, in the view of either the investigator or sponsor, it results in any of the following outcomes:

- Death;
- A life-threatening AE;

Note: An AE is considered "life-threatening" if, in the view of either the investigator or sponsor, its occurrence places the subject at immediate risk of death. It does not include an AE that, had it occurred in a more severe form, might have caused death.

The AE reporting period ends upon study exit. Study drug includes the investigational drug under evaluation and vehicle given during any stage of the study. All AEs will be coded using the MedDRA 21.0.

Treatment-emergent adverse events (TEAEs) are defined as any adverse event that occurs or worsens after the first dose of study treatment. AEs recorded in the eCRF which began prior to treatment will not be included in the summary tables but will be included in the AE data listings.

An overall summary will be presented that includes the number of AEs, TEAEs, serious AEs (SAE), and serious TEAEs (TE-SAE). The summary will also include the number and percentage of subjects withdrawn due to an AE, the number and percentage of subjects with an AE resulting in death, and the number and percentage of subjects who experienced at least one AE, TEAE, SAE and TE-SAE, by treatment group and for all subjects. This summary will include breakdowns of AEs further categorized as ocular or non-ocular. The summary will also include the number and percentage of resolved ocular AEs, and the mean number of days until AE resolution for resolved ocular AEs.

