Additional summaries of TEAEs will be provided showing the number and percentage of subjects who experienced at least one TEAE. These summaries will be presented by SOC and PT. Non-ocular TEAEs will be summarized using discrete summary statistics and presented by treatment group at the subject and event level by SOC and PT. Ocular TEAEs will be similarly summarized at the subject and event level as well as for study and fellow eyes separately. If a subject reports the same PT multiple times within the same SOC, that PT will only be reported once within that SOC. As with the PT, if a subject reports multiple conditions within the same SOC, that SOC will only be reported once. In the summary, SOC will be listed in order of descending frequency for all subjects; PTs will be listed in order of descending frequency for all subjects within each SOC. The occurrence of non-ocular and ocular TEAEs will also be tabulated by SOC, PT, and maximal severity, as well as by study day of onset (prior to Day 15, Day 15 to Day 43, After Day 43).

Separate summaries will be provided for the following categories of AEs:

- Ocular TEAEs
- Non-ocular TEAEs
- Treatment-related ocular TEAEs
- Treatment-related non-ocular TEAEs
- SAEs

Summaries of TEAEs by maximal severity will be presented for ocular AEs and non-ocular AEs separately. The number of subjects with any TEAEs (along with percentages) will be tabulated by SOC and PT within each SOC by treatment group. To count the number of subjects with any TEAEs, if a subject has multiple TEAEs coded to the same PT within the same SOC, the subject will be counted once under the maximal severity.

All TEAEs with possible, probable, and definite relationship to IP are considered as treatment-related TEAEs.

All AEs will be presented in a subject listing that classifies each AE as ocular or non-ocular and indicates whether it is a TEAE. Separate listings will be produced for AEs leading to study discontinuation, AEs leading to death and SAEs.

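### TEAE summaries by arm are event counts and crude percentages of everyone dosed; if observation time differs between arms, the percentages favour the arm observed for less time

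*SAP*

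**What the plan says.** Safety and tolerability compared with vehicle is a primary objective of both stages (Protocol Table 4-1; SAP section 2). Protocol 12.4.7 describes the main summary: "Incidence rates of each treatment-emergent adverse event will be summarized by primary system organ class and preferred term". SAP 16.1 makes this concrete: "Additional summaries of TEAEs will be provided showing the number and percentage of subjects who experienced at least one TEAE". TEAEs are also counted at event level, and tabulated by maximal severity and by onset window (before Day 15, Day 15 to 43, after Day 43). No denominator is given for the onset windows.

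The analysis set is defined in SAP 7.4: "The Safety population includes all randomized subjects who have received at least one dose of the investigational product". Time on study plays no part in it.

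Three provisions determine how long a patient is observed:

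- SAP 16.1 states: "The AE reporting period ends upon study exit".
- Protocol 10.2.2 exits patients who need rescue.
- Protocol 6.1 states: "Groups that are either unsafe, poorly tolerated, or likely futile may be discontinued by the DRC". Under Protocol 13.7.6 the committee meets at least monthly.

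Other text lengthens observation. For Stage 1, Protocol 6.1 says "Patients already enrolled in Stage 1, Cohort 1 will continue at the investigator's discretion" when the first dose is judged not tolerated, and adds "Any patients that discontinue during the study will be followed through the resolution of their adverse event(s) or end of study". Protocol 11.5 covers serious events during the study period "and for at least 12 weeks after the last dose of study drug must be immediately reported".

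The SAP also plans exposure in days by arm (12.2), reasons for discontinuation (section 9) and withdrawals due to an AE (16.1). None of these is linked to the incidence tables.

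**The concern.** A crude percentage compares arms fairly only if patients in each arm are observed for about the same time. This design has foreseeable ways for that to fail. In Stage 2, one TID vehicle group is the comparator for the 50, 30 and 3 mg/mL TID groups (SAP 3.1 and 8.4), so discontinuing one dose does not discontinue its control. Exit for rescue may also differ by arm.

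The bias can run either way. A dose group observed for less time would show too low a percentage. If vehicle patients leave more often for worsening dry eye, vehicle is observed for less time and the drug looks worse than it is. The exposure and withdrawal tables would reveal unequal follow-up, but they do not correct the percentages.

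**Working it through.** **Plan's own figures.** The documents give no AE rate, onset pattern, probability of a halt or safety power, so there is no AE figure to reproduce. The one relevant planning value is the 10% dropout in Protocol 12.1 (103 × 0.9 = 92.7, rounded to 93; 67 × 0.9 = 60.3, rounded to 60). All AE rates below are assumptions.

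**Crude percentage under unequal follow-up.** Assume a constant hazard, 85 planned days, 20% on vehicle and a true rate ratio of 2.

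- Vehicle hazard: −ln(0.80)/85 = 0.002625 per day. Active hazard: 0.005250 per day.
- Crude percentage for an arm seen for T days: 1 − exp(−hazard × T).
- If a share f leaves at Day 15: f × 7.6% + (1 − f) × 36.0%.

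| Active arm | Crude % active | Crude % vehicle |
|---|---|---|
| Full follow-up | 36.0 | 20 |
| 25% leave at Day 15 | 28.9 | 20 |
| 50% leave at Day 15 | 21.8 | 20 |
| 75% leave at Day 15 | 14.7 | 20 |
| All leave at Day 43 | 20.2 | 20 |
| All leave at Day 15 | 7.6 | 20 |

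The percentages coincide when the whole active arm is seen for 85/(rate ratio) days: 56.7 for a ratio of 1.5, 42.5 for 2 and 28.3 for 3. A smaller excess can reverse. With a true 30% at 84 days (hazard −ln(0.70)/84 = 0.004246), 42 days of follow-up shows 16.3%, below a 20% vehicle arm.

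**Equal exits.** If 10% of each arm leaves at Day 15, active shows 0.1 × 7.6 + 0.9 × 36.0 = 33.2%. Vehicle shows 0.1 × 3.9 + 0.9 × 20 = 18.4%. The ratio stays at 1.80, as with full follow-up (36.0/20).

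**Early-onset events.** If 80% of TEAEs start before Day 15, an active arm cut entirely at Day 15 still shows 0.8 × 36 = 28.8% against 20%. The excess is reduced but visible.

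**Onset windows.** Take the case where half the arm leaves at Day 15. First events after Day 43 among those still observed are exp(−0.00525 × 43) − exp(−0.00525 × 85) = 15.8%. Divided by everyone dosed, this becomes 7.9%, against 9.3% on vehicle. With subjects still under observation as the denominator, it is 15.8% against 9.3%.

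**Cumulative incidence.** In the same case, Kaplan-Meier at Day 85 estimates 36.0% against 20%. If the whole arm leaves at Day 43, the comparison is made at Day 43: 20.2% against 1 − exp(−0.002625 × 43) = 10.7%.

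**Why not a rate per patient-month.** Take two identical arms, each with 20% incidence by Day 84 and exponential onset with mean 14 days, truncated at 84: F(t) = 0.20 × (1 − e^(−t/14))/(1 − e^(−6)). One arm is followed for 84 days.

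| Days observed | F(t) | Days at risk per patient | Events per day at risk | Ratio to 84 days |
|---|---|---|---|---|
| 84 | 20.0% | 70.0 | 0.00286 | 1.00 |
| 42 | 19.1% | 36.2 | 0.00526 | 1.84 |
| 14 | 12.7% | 13.0 | 0.00977 | 3.42 |

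At 42 days the crude figure (19.1% against 20%) is nearly unbiased, while the person-time rate shows a false ratio of 1.84.

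**The case against.** The strongest reply is that nothing in the documents shortens observation in a halted group. A Stage 1 halt stops expansion, and patients already enrolled may continue. The initial cohort is only 8 active and 2 vehicle patients, too few for any adjusted measure to be informative. Discontinued patients are followed to AE resolution or end of study, and serious events are reported for at least 12 weeks after the last dose. Protocol 12.4.8 mentions termination of dose groups alongside the interim analysis, after the last Stage 1 Month 3 visit. AE tables carry no between-arm test, event counts are given as well as percentages, and short exposure and AE withdrawals would be visible by arm.

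Much of this stands. A reader might infer that an arm halted for harm is necessarily watched for less time. The documents do not say so, and for a Stage 2 group they are silent on whether enrolled patients stay to Day 85. A reader might also infer that departed patients count as event-free in the later onset windows; the SAP leaves that denominator unspecified. The incidence rates in Protocol 12.4.7 may simply mean percentages of subjects, so no person-time measure was necessarily promised.

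The reply does not remove the gap. Following a known event to resolution does not by itself capture new events, and the serious-event window does not cover non-serious TEAEs. The exposure and withdrawal tables show unequal observation but do not let a reader recover a comparable incidence. Percentages by arm will be compared whether or not a test is attached.

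**Conclusion.** The point holds as a contingent weakness that is cheap to repair. SAP 16.1 has no subject-level TEAE measure that takes account of time under observation, and the plan permits observation time to differ between an active group and its vehicle.

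With equal exits and the planned 10% dropout the effect is small. It becomes material only if a sizeable share of one arm leaves early and events continue to arise through the 12 weeks. In the constant-hazard example with a true ratio of 2, roughly half the arm leaving at Day 15, or all of it at about Day 43, hides the excess. Front-loaded events largely protect the crude figure. These sizes rest on assumed rates and onset patterns.

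The stronger reading, that a harmful arm will look as safe as vehicle, is not supported: it needs heavy truncation and late or evenly spread events, and no passage prescribes early exit.

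**What to change.** In SAP 16.1:

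1. Keep the crude n (%) and event counts.
2. In the onset tables (14.3.1.11.x and 14.3.1.12.x), use the number of subjects still under observation at the start of each interval as the denominator.
3. For any ocular, any non-ocular and any treatment-related TEAE, add a Kaplan-Meier cumulative incidence of first event by arm, censored at the end of AE observation. Give the difference from matched vehicle with a 95% CI at Day 15, Day 43 and Day 85, or at the latest of these that both arms reach.
4. Do not make a per-patient-month rate the headline measure.

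Reconcile Protocol 6.1 and 11.5 with SAP 16.1 on when AE and SAE observation ends, and state what applies to patients in a discontinued group, so that the censoring date matches the events counted.

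The cost is SAP wording and extra table columns. The completion or discontinuation date is already used in SAP 12.2, though it serves as the censoring date only if the reconciled text ends AE observation there. Censoring at exit assumes that exit carries no information about later AEs. That is doubtful for patients who leave because of an AE or rescue, so the curves should be read beside the withdrawal counts.

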Summary of Visit Schedule:	5 visits over the course of approximately 14 weeks 
• Visit 1 = Screening (Day -14 ± 2)• Visit 2 = Baseline & Randomization, Day 1• Visit 3 = 2-Week Follow-Up (Day 15 ± 2)• Visit 4 = 1.5 Month Follow-up (Day 43 ± 2)• Visit 5 = 3 Month Follow-up (Day 85 ± 2)
Measures Taken to Reduce Bias:	This is a randomized treatment assignment, double-masked study
Study Population Characteristics:	
Number of Subjects:	
Stage 1:
 
The total number of randomized patients for Stage 1 of the study will be approximately 100 at up to 2 sites. Approximately 50% of patients should have a baseline eye dryness score of ≥ 60 and approximately 50% of patients should have a baseline inferior corneal staining score (ICCS) > 1.5 according to the Ora Calibra® staining scale. Based upon data from Xiidra®, OPUS 2 a screen failure rate of $\sim 50\%$ is expected. Thus, ~ 200 patients will need to be screened to achieve ~ 100 patients randomized to treatment.
 
Stage 2:
 
The total number of randomized patients for Stage 2 of the study will be approximately 330 (see Figure 6.1-1, Stage 2) at up to 7 sites. Approximately 50% of patients should have a baseline eye dryness score of ≥ 60 and approximately 50% of patients should have a baseline inferior corneal staining score (ICCS) > 1.5. Based upon data from Xiidra®, OPUS 2 a screen failure rate of $\sim 50\%$ is expected. Thus, ~ 660 patients will need to be screened to achieve ~ 330 patients randomized to treatment.
 
Note: patients can be reallocated from discontinued groups to increase the power in groups that are continued at the discretion of the DRC.

Condition/Disease:	Dry Eye Disease (DED)

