10.3.1.5 Visit 5: 3 Month Follow-up (Day 85 ± 2 Days)

Pre-CAE®

- Study drug collection
- Medical/medication history update
- Urine pregnancy test (for females of childbearing potential)

- Patient symptoms using the visual analog scale
- Ocular Discomfort Score
- OSDI
- SANDE
- BCVA with manifest refraction
- Vital signs
- Bulbar conjunctival hyperemia scores (Ora Calibra® Conjunctival Redness for Dry Eye Scale)
- Slit-lamp biomicroscopy
- Tear Collection (selected sites)
- Oculus Keratograph 5® procedures: TBUT and tear meniscus height (selected sites)
- TFBUT
- Sodium fluorescein corneal staining, using the Oxford scale and Ora Calibra® scales
- Lissamine green conjunctival staining, using the Oxford scale
- 15+ minute wait from end of Lissamine staining to start of Schirmer's Test
- Schirmer without anesthesia
- 90-minute CAE® exposure;
 - Ora Calibra® Ocular Discomfort Scale upon entering the CAE® and every 5 minutes thereafter;

Post-CAE®

- Patient symptoms using the Visual Analog Scale
- Ocular Discomfort Score

- Bulbar conjunctival hyperemia scores (Ora Calibra® Conjunctival Redness for Dry Eye Scale)
- Slit-lamp biomicroscopy
- TFBUT
- Sodium fluorescein corneal staining, using the Oxford scale and Ora Calibra® scales
- Lissamine green conjunctival staining, using the Oxford scale
- Intraocular pressure (IOP)
- Ophthalmoscopy
- Blood sample collection for Hematology and Chemistry
- Urine sample collection for Urinalysis
- Administer AXR-159 Ophthalmic Solution or vehicle in both eyes (must NOT be done before blood and tear sample collection)
- Ora Calibra® Drop Comfort Assessment
- Adverse event query
- Study Exit

Adverse Events (AEs) (both elicited and observed) will be monitored throughout the study. All AEs (both elicited and observed) will be promptly reviewed by the investigator for accuracy and completeness. All AEs will be documented on the appropriate CRF.

If a female becomes pregnant during the study, the investigator will notify AxeroVision Inc. immediately after the pregnancy is confirmed and the patient will be exited from the study after appropriate safety follow-up. The investigator will (1) notify the patient's physician that the patient was being treated with an investigational drug (AXR-159 Ophthalmic Solution), and (2) follow the progress of the pregnancy. The investigator must document the outcome of the pregnancy and provide a copy of the documentation to AxeroVision Inc.

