TABLE 14.3.1.6.2	ALL OCULAR TREATMENT-RELATED TREATMENT-EMERGENT ADVERSE EVENTS – STAGE 2	SAFETY POPULATION
TABLE 14.3.1.6.3	ALL OCULAR TREATMENT-RELATED TREATMENT-EMERGENT ADVERSE EVENTS – COMBINED STAGE 1 AND STAGE 2	SAFETY POPULATION
TABLE 14.3.1.7.1	ALL NON-OCULAR TREATMENT-RELATED TREATMENT-EMERGENT ADVERSE EVENTS – STAGE 1	SAFETY POPULATION
TABLE 14.3.1.7.2	ALL NON-OCULAR TREATMENT-RELATED TREATMENT-EMERGENT ADVERSE EVENTS – STAGE 2	SAFETY POPULATION

Table Number	Title	Population
TABLE 14.3.1.7.3	ALL NON-OCULAR TREATMENT-RELATED TREATMENT-EMERGENT ADVERSE EVENTS – COMBINED STAGE 1 AND STAGE 2	SAFETY POPULATION
TABLE 14.3.1.8.1	ALL SERIOUS ADVERSE EVENTS – STAGE 1	SAFETY POPULATION
TABLE 14.3.1.8.2	ALL SERIOUS ADVERSE EVENTS – STAGE 2	SAFETY POPULATION
TABLE 14.3.1.8.3	ALL SERIOUS ADVERSE EVENTS – COMBINED STAGE 1 AND STAGE 2	SAFETY POPULATION
TABLE 14.3.1.9.1	ALL OCULAR TREATMENT-EMERGENT ADVERSE EVENTS BY MAXIMAL SEVERITY – STAGE 1	SAFETY POPULATION
TABLE 14.3.1.9.2	ALL OCULAR TREATMENT-EMERGENT ADVERSE EVENTS BY MAXIMAL SEVERITY – STAGE 2	SAFETY POPULATION
TABLE 14.3.1.9.3	ALL OCULAR TREATMENT-EMERGENT ADVERSE EVENTS BY MAXIMAL SEVERITY – COMBINED STAGE 1 AND STAGE 2	SAFETY POPULATION
TABLE 14.3.1.10.1	ALL NON-OCULAR TREATMENT-EMERGENT ADVERSE EVENTS BY MAXIMAL SEVERITY – STAGE 1	SAFETY POPULATION
TABLE 14.3.1.10.2	ALL NON-OCULAR TREATMENT-EMERGENT ADVERSE EVENTS BY MAXIMAL SEVERITY – STAGE 2	SAFETY POPULATION
TABLE 14.3.1.10.3	ALL NON-OCULAR TREATMENT-EMERGENT ADVERSE EVENTS BY MAXIMAL SEVERITY – COMBINED STAGE 1 AND STAGE 2	SAFETY POPULATION
TABLE 14.3.1.11.1	ALL OCULAR TREATMENT-EMERGENT ADVERSE EVENTS BY STUDY DAY OF ONSET – STAGE 1	SAFETY POPULATION
TABLE 14.3.1.11.2	ALL OCULAR TREATMENT-EMERGENT ADVERSE EVENTS BY STUDY DAY OF ONSET – STAGE 2	SAFETY POPULATION
TABLE 14.3.11.3	ALL OCULAR TREATMENT-EMERGENT ADVERSE EVENTS BY STUDY DAY OF ONSET – COMBINED STAGE 1 AND STAGE 2	SAFETY POPULATION
TABLE 14.3.1.12.1	ALL NON-OCULAR TREATMENT-EMERGENT ADVERSE EVENTS BY STUDY DAY OF ONSET – STAGE 2	SAFETY POPULATION
TABLE 14.3.1.12.2	ALL NON-OCULAR TREATMENT-EMERGENT ADVERSE EVENTS BY STUDY DAY OF ONSET – STAGE 2	SAFETY POPULATION
TABLE 14.3.1.12.3	ALL NON-OCULAR TREATMENT-EMERGENT ADVERSE EVENTS BY STUDY DAY OF ONSET – COMBINED STAGE 1 AND STAGE 2	SAFETY POPULATION
TABLE 14.3.2.1	ORA CALIBRA® DROP COMFORT SCALE – STAGE 1	SAFETY POPULATION
TABLE 14.3.2.2	ORA CALIBRA® DROP COMFORT SCALE – STAGE 2	SAFETY POPULATION

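### TEAE onset tables use periods of about 14, 29 and 42 days with no person-time or number at risk, so comparing periods within an arm misleads

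*SAP*

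**What the plan says.** SAP 16.1 gives the governing measure for its TEAE tables: "Additional summaries of TEAEs will be provided showing the number and percentage of subjects who experienced at least one TEAE". It also plans event-level counts. It then adds tabulation by SOC, preferred term and maximal severity, "as well as by study day of onset (prior to Day 15, Day 15 to Day 43, After Day 43". SAP Section 20 lists the resulting tables, for example "ALL OCULAR TREATMENT-EMERGENT ADVERSE EVENTS BY STUDY DAY OF ONSET – STAGE 1".

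The clock is set elsewhere. A TEAE is "any adverse event that occurs or worsens after the first dose of study treatment". The Protocol synopsis has "Visit 2 = Baseline & Randomization, Day 1" and "Visit 5 = 3 Month Follow-up (Day 85 ± 2". SAP 16.1 adds: "The AE reporting period ends upon study exit".

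SAP 12.2 derives exposure in days for each subject, but only as a separate summary. Nothing in the SAP divides adverse events by exposure or by the number still at risk. The onset tables have no stated denominator. The SAP reports a repeated preferred term once per subject, but does not say whether that rule applies within each onset period or over the whole study.

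**The concern.** A table by time of onset is read across its columns, to see whether events come early, late or steadily. Here the last column covers three times as many days as the first, so a term with a constant rate prints as one that rises with time on treatment. Conversely, equal percentages in the three columns would mean a falling rate.

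Safety and tolerability lead the primary objective in both stages, and these are the only planned summary tables of adverse events by time of onset. SAP Section 20 sends tables labelled Stage 1 to the interim analysis, so the ocular Stage 1 version will be in front of those deciding which groups go forward.

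**Working it through.** **Inputs.** First dose on Day 1 and last visit on Day 85 ± 2 (Protocol synopsis); cut points from SAP 16.1; 10% dropout from SAP Section 5. The documents give no adverse event rate, so the cumulative incidence P by Day 85 is an assumption, varied from 1% to 50%. There is no figure in the plan to reproduce on this point.

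**Period lengths.** Days 1-14 give 14 days. Days 15-43 give 43 − 15 + 1 = 29 days. Days 44-85 give 85 − 43 = 42 days. The ratio is 1 : 2.07 : 3.00. With the ± 2 day window the last period is 40 to 44 days, or 2.86 to 3.14 times the first.

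**Constant hazard.** λ = −ln(1 − P)/85 per day.

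- Any onset in a period of L days, fixed N: 1 − exp(−λL).
- First onset only, period from day a to day b: exp(−λa) − exp(−λb), with (a, b) = (0, 14), (14, 43), (43, 85).
- Dropout reaching 10% by Day 85: hazard d = −ln(0.9)/85. For a period starting after s days, the any-onset percentage on fixed N is exp(−ds) × λ/(λ + d) × [1 − exp(−(λ + d)L)]. For first onset only, exp(−ds) becomes exp(−(λ + d)s).

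For P = 10%, λ = 0.10536/85 = 0.00124 per day, and the three any-onset percentages are 1.72, 3.53 and 5.07.

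| P | Any onset, % in periods 1, 2, 3 | Last/first | With dropout | First onset only | First onset, with dropout |
|---|---|---|---|---|---|
| 1% | 0.17, 0.34, 0.50 | 3.00 | 2.79 | 2.98 | 2.78 |
| 5% | 0.84, 1.73, 2.50 | 2.97 | 2.77 | 2.90 | 2.70 |
| 10% | 1.72, 3.53, 5.07 | 2.95 | 2.75 | 2.80 | 2.61 |
| 20% | 3.61, 7.33, 10.44 | 2.89 | 2.70 | 2.58 | 2.41 |
| 50% | 10.79, 21.06, 29.00 | 2.69 | 2.51 | 1.89 | 1.77 |

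The last four columns are last-to-first ratios. Event counts with 10% dropout give 2.80, so the event-level figures do not remove the effect.

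**The reverse case.** Equal percentages of 5% in each period, divided by 2, 29/7 and 6 weeks, are 2.5, 1.2 and 0.8 per 100 patient-weeks. That is a threefold fall in rate.

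**After adjustment.** At P = 10% the rate is 0.124 per 100 subject-days, or 0.87 per 100 patient-weeks, in every period. The last-to-first ratio becomes 1.0.

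**Between arms.** Window length is common to both arms and cancels. A fixed N does not cancel if dropout differs. As an illustration, suppose 20% of active and 5% of vehicle subjects have left by Day 43, and the late risk is 5.07% in both arms. The last column then reads 0.80 × 5.07 = 4.1% against 0.95 × 5.07 = 4.8%.

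**The case against.** The strongest reply is that the trial is vehicle-controlled and the tables are by treatment group. A constant background rate climbs identically in the vehicle column, so a reader who compares arms is not misled by window length. That stands. A reader might infer that the tables bias the comparison of drug with vehicle, but the documents support this only if dropout differs between arms and N is fixed.

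Nor do the main safety results depend on these tables. Protocol Table 4-1 lists overall TEAE incidence, treatment-related TEAEs and shift tables, and no test or decision rule uses the onset tables. The Stage 1 expansion decision is taken at Week 2.

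A reader might also infer that a fading instillation reaction would be hidden. That goes too far. A reaction that starts with the first drops falls in the first column whatever the denominator. A hazard that halves in each period prints as about 4.9%, 5.1% and 3.7%, which understates the fall but ends lower. Drop comfort (SAP 16.2) and slit-lamp findings (SAP 16.4) by visit also bear on timing.

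The "90-minute CAE® exposure" and the second adverse event query at Visit 5 might suggest that the last column is inflated further. The schedule also works the other way. No visit falls between Day 43 and Day 85, so the last period relies on the longest recall and may miss transient events. Neither effect can be sized from the documents, and the net direction is unknown.

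Finally, the counts are small. With about 50 active subjects in Stage 1 (the SAP expects 43 to 53) and P = 10%, the columns would hold about 0.9, 1.8 and 2.5 patients. That limits how much any single row can mislead, but does not make the columns comparable.

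**Conclusion.** The point holds for comparison across periods within an arm. For uncommon preferred terms, with cumulative incidence up to about 10%, a constant hazard gives a last-to-first ratio of about 2.6 to 3.0 under every counting rule tried at the planned Day 85. For common events or an any-TEAE row it is smaller, about 1.8 to 1.9 at 50% incidence if subjects count only at first onset.

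This rests on three assumptions: a constant hazard, a fixed denominator (inferred from the general measure in SAP 16.1), and Day 1 as the start of the TEAE clock, in line with the exposure formula in SAP 12.2. SAP 16.1 also says that study drug includes vehicle given at any stage. If run-in vehicle started the clock, the first period would be about 28 days and the length ratio 42/28 = 1.5.

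It is a defect of presentation in descriptive tables. It does not undermine the overall safety comparison. It is worth correcting because these tables exist to show timing and the correction is cheap.

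**What to change.** In SAP 16.1 and Tables 14.3.1.11.x and 14.3.1.12.x:

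- Use as the denominator the subjects still on study at the start of each period, and print that number.
- State whether a subject counts once per period or only at first onset.
- Add subjects with an event, or events, per 100 patient-weeks in each period by arm, with the active-minus-vehicle difference. Say which of the two is used and how time at risk is counted.

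Do not add a separate line for onset during or after the CAE. The adverse event record specifies a date of onset and no clock time, so events before and after the exposure on the same day cannot be told apart. At most, flag TEAEs with onset on the Visit 5 date.

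The cost is SAP wording, one derived denominator and slightly wider tables. Onset dates and completion or discontinuation dates are already collected, so no new data are needed. The same edit could correct the title of Table 14.3.1.12.1, which is labelled Stage 2 like Table 14.3.1.12.2, so that no non-ocular onset table is listed for Stage 1.
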